# **Trial Design**

A two-group design is appropriate:

Those mothers who score above the cut-off point on the EPDS and the GAD 7 with depression or anxiety will receive psychiatric assessment plus medication (if needed) plus a monthly phone call by a midwife, plus 12 sessions of systemic therapy in the **Intervention Group** 

And a psychiatric assessment plus medication (if needed) plus a monthly phone call by a midwife in the **Control Group** 

The outcomes

AN Mothers who score above the cut-off point on the EPDS and the GAD 7

with anxiety and depression in the Intervention Group will have a better outcome reflected through:

- (i) a lower and statistically significant score on the EPDS and GAD7 when compared to those in the control group
- (ii) a higher statistically significant score on the Dyadic Adjustment Scale Revised (R-DAS) when compared to those in the Control Group

The allocation ratio is intended to be as follows:

**60 mothers**; (30 ANmothers will be in the intervention group, whereas **30**ANmothers will be in the control group)

During the screening process, AN mothers who score above the cutoff point in the EPDS and the GAD7 will be put in one cluster. The randomisation into the intervention and the control group will take place through the process described below.

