# **Participants**

#### Inclusion Criteria

- 1. Batches of 100 and later 150 mothers belonging to the 9 firms within the Gynae Outpatients Antenatal Clinic will be universally screened for mental health difficulties usually during the 12th week of pregnancy before the 19th week. The rationale behind the latter time frame is meant to give sufficient time for the intervention to take place before delivery.
- 2. Same-sex couples will be included.
- 3. A mother who scores as depressed on the EPDS or anxious on the GAD7 will be eligible to proceed for further psychiatric assessment through the MINI
- 4. AN Mothers who during their pregnancy are self referred or are referred by professionals to the Perinatal Mental Health Service (PMHS)

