# TRIAL FLOW CHART – ( Mental Health Cluster) ANTENATAL MOTHERS

At antenatal period (after 12 weeks pregnancy during first booking visit), a batch of 100 mothers who happen to have the booking appointment at the time of distribution of the screening sheets are asked to complete the Phase I assessment including brief Demographic Data, Whooley Questions & Relationship Questions. Screening sheets sent by post prior to first booking appointment.

Mothers with no Mental Health Difficulties receive treatment as usual from Gynae and Obs. Mothers with Mental Health Difficulties are asked by the recruiter, normally a midwife to complete Phase II assessment (including EPDS, GAD7, R-DAS, ANRQ). Those scoring for anxiety and/or depression are assessed through the MINI for a diagnosis by psychiatrist/clinical psychologist making use of the MINI

Antenatal mothers who are diagnosed with anxiety or depression and are willing to participate in the RCT, will form part of the Mental Health Cluster of this study. 60 mothers will be randomised:

- a. 30 in intervention group
- b. 30 in control group

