#### Measures

All Pre-Measures will take place before the interventions for all participants prior to randomisation into intervention and control groups respectively.

Post measures will take place after the intervention which is of 19 weeks duration.

We will evaluate such an outcome with the following pre-post measures.

Pre Measures:

(i)EDPS for prenatal and postnatal depression of the parents

The Edinburgh Postnatal Depression Scale (EPDS) is one of the most widely used screening instruments for assessing symptoms of perinatal depression and anxiety both in a clinical setting and also for research purposes (Gibson et al, 2009; Kozinsky and Dudas, 2015).

It is a 10-item scale written in the past tense with four possible responses graded according to the severity and duration of the symptom during the previous seven days. The scoring method is simple: 0 for absence of the symptom; 3 for maximum severity and duration; 1 and 2 which were intermediate. The total score ranged from 0 to 30.

This self-reporting instrument was originally developed in the U.K. Cox et al, (1987) specifically for childbearing women. The popularity of this brief instrument reflects the original British validation study

in which nine out of ten women who were diagnosed by a psychiatrist as being depressed after giving birth were correctly identified in a blinded comparison with scores above a cut-off on the EPDS. The psychometric properties of the EPDS in primary health care were: 86 % sensitivity (correctly identifying true cases), 78 % specificity (correctly identifying people without the condition) and 73 % positive predictive value (proportion of respondents scoring positive in the test who had a mental disorder diagnosed by clinical interview) (Cox et al, 1987).

The EPDS was acceptable to women, took only 5 minutes to complete and was rapidly scored. It screens only for depression and those who score below the cut-off should not be assumed to have no psychiatric disorder. A higher response rate (95%) is obtained when the EPDS is sent by post and careful follow-up of non-responders is carried out (Cox et al, 1993).

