Pre-and post-means, medians, and standard deviations for all the measures, namely the GAD-7, EPDS and R-DAS will be compared and analysed between the respective groups, namely for the intervention and control group participants. Descriptive measures will also be presented visually using boxplots comparing pre-and post- test scores for each group. The paired samples t-test can be used to compare the mean scores of the pre-and post-sessions of both groups. If the differences of the pre-post measures deviate from the normality assumption, the Wilcoxon Signed-Ranks test should then be used to compare the scores between the pre-post periods for both intervention and control groups. The change of the pre- and post-test scores can be categorized into three groups as no change, lower

post-test score and higher post-test score and compared through the Chi-Square test between intervention and control to assess whether the increase or decrease in the post-test score is differing among the two groups.

Next, to assess the effect of the study condition, there are three adequate ways to analyse a numerical outcome (GAD-7, EPDS and R-DAS) where the common point of these approaches is that the prescores must be considered (the best approach will be chosen accordingly):

- 1. Independent samples-test on change of scores (i.e., the post-minus-pre differences), assuming the normality assumption is satisfied. The overall test is statistically significant if it yields a sufficiently small p-value. Following the hypothesis testing, the Cohen's d effect size statistic will be calculated for intervention effects. If a nonparametric approach is chosen (assuming normality assumption is deviated), the Mann-Whitney test should be performed on change scores. The effect size for the Mann-Whitney U test is calculated by dividing the standardised test statistic z and square root of the number of pairs n.
- 2. Two-way mixed-model ANOVA with group as between-subjects factor (intervention and control groups) and time-point as within-subject factor (i.e., repeated measures; with two levels, baseline, and post-intervention). Note that the p-value for interaction in this design will be equivalent to the p-value from the independent samples t-test on change scores mentioned in (1). This will also answer the essential question of the study: do the changes from baseline differ between the groups?

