- 3. Analysis of covariance (ANCOVA) of post-intervention scores with baseline score as the covariate. This approach differs subtly from the two mentioned above. Analysis of covariance treats the pre-test value as a covariate that can be a source of variation that may influence post-test scores, and accordingly the post-test score is regressed on both the pre-test score and the grouping variable. ANCOVA adjusts the pre-test scores, increasing the power to determine whether or not there has been a treatment effect. This approach tests the null hypothesis of no difference between the control and treatment post.

Should the results indicate that there has been significant improvement at post-testing, one should also evaluate for any differences in the change of scores between the two groups through stepwise linear regression using a bootstrapping procedure with 5000 replications recommended for analyses with smaller sample sizes (Preacher and Hayes, 2008). Groups alone will be included in Model 1, and any confounds that differed across the two groups at baseline will be included in Model 2, allowing for the comparison of the effect size as a function of study condition in unadjusted and adjusted models. Results will be determined to be statistically significant if p values were <0.05.

Furthermore, it would be of interest to see whether there is an association between a high score in ANRQ and the incidence of depression and anxiety. Thus, the idea is to check for any possible correlation between ANRQ and EPDS and ANRQ and GAD-7 for both pre- and post-testing, through the Pearson correlation or alternatively the Spearman correlation, if the assumption of normality is not satisfied.

The assumption of normality to perform all the above tests will be evaluated by the Shapiro-Francia test. If the assumption of normality has been violated, the p-value will be less than 0.05. If the assumption of normality has not been violated, the p-value will be greater than 0.05. This is because the Shapiro-Wilk test is evaluating the null hypothesis that the distribution of the data is equal to a normal distribution. Rejecting the null hypothesis means that the distribution of the data is not equal to a normal distribution.

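### Within-arm pre-post significance tests are planned for all three scales; they cannot show an effect of therapy, and for EPDS and GAD-7 a fall is expected in both arms without one

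*Protocol*

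**What the plan says.** The tests. In the Protocol, Analytic Methods, after the means, medians, standard deviations and boxplots, comes "The paired samples t-test can be used to compare the mean scores of the pre-and post-sessions of both groups". If the differences are not normal, "the Wilcoxon Signed-Ranks test should then be used to compare the scores between the pre-post periods for both intervention and control groups". The scales named are GAD-7, EPDS and R-DAS.

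The baseline. Under the Trial Flow Chart, mothers with mental health difficulties "complete Phase II assessment (including EPDS, GAD7, R-DAS, ANRQ). Those scoring for anxiety and/or depression are assessed through the MINI". Under Measures, "All Pre-Measures will take place before the interventions for all participants prior to randomisation into intervention and control groups respectively". The list for Intervention Group mothers says that both arms repeat EPDS, GAD-7 and the dyadic scale after 19 weeks. No second assessment between qualification and randomisation is described. That Phase II is the pre-score is a strong inference, though no single sentence says so.

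The entry rule is given in two ways. Inclusion Criteria: "A mother who scores as depressed on the EPDS or anxious on the GAD7 will be eligible" for the MINI assessment. Trial Design refers to "AN Mothers who score above the cut-off point on the EPDS and the GAD 7".

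The effect of therapy. Analytic Methods then lists three between-arm analyses: a test on change scores, a two-way mixed ANOVA, and ANCOVA of the post score on baseline. It leaves the choice among them open, and says that the essential question is whether change differs between the arms.

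**The concern.** A baseline that was selected for being high tends to be lower when measured again. This regression to the mean is the same in expectation in both arms. To it may be added the natural course over 19 weeks and the care common to both arms: psychiatric assessment, medication if needed, and a monthly midwife call. A paired test in one arm asks only whether the mean changed. Rejecting that null carries no information about systemic therapy.

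Two misreadings are at stake. A significant fall in the therapy arm may be reported as benefit. Or a significant fall in the therapy arm beside a non-significant one in the control arm may be read as a difference between the arms. At 30 per arm the second pattern arises easily by chance.

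**Working it through.** **Inputs from the Protocol**
- Arm size: "30 in intervention group", and the same number in control.
- Level: "Results will be determined to be statistically significant if p values were <0.05". Sidedness is not stated; two-sided is taken here.
- GAD-7: further evaluation at 10 or more (Measures).
- EPDS: the Maltese antenatal cut-off recommended under Measures is 13/14, taken as 14 or more. The trial's own cut-off is not fixed.
- GAD-7 one-week English-Maltese agreement: ICC 0.819 (Measures).

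**Assumptions, not in the Protocol**
- GAD-7 in the pool that completes Phase II: mean 5 with SD 4.5, or mean 8 with SD 5.
- EPDS: mean 7 or 10, SD 5. EPDS/GAD-7 correlation 0.7.
- 19-week pre-post correlation ρ from 0.5 to 0.82. The upper end borrows the one-week agreement, which is optimistic for 19 weeks.
- No effect of any care and no natural change, unless stated.

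**Step 1. The Protocol's own figure.** For two administrations, ICC = (F − 1)/(F + 1) = (10.071 − 1)/(10.071 + 1) = 9.071/11.071 = 0.819. It reproduces. The Protocol gives no figure for the expected pre-post change.

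**Step 2. Single scale, closed form.** With entry k SDs above the mean, let λ = φ(k)/(1 − Φ(k)) and v = 1 + kλ − λ². Then:
- expected fall = (1 − ρ) × λ × SD
- SD of change = SD × √[(1 − ρ)²v + 1 − ρ²]
- P(one arm significant) comes from the noncentral t on 29 df, with noncentrality (fall/SD of change) × √30
- the arms are independent under the null, so P(both) = P² and P(therapy only) = P(1 − P)

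GAD-7 mean 5, SD 4.5, ρ = 0.5: k = 1.11, λ = 1.615, v = 0.187. Fall = 0.5 × 1.615 × 4.5 = 3.6 points; SD of change 4.0; ratio 0.905; P = 0.998; both arms 0.995.

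GAD-7 mean 8, SD 5, ρ = 0.819: k = 0.4, λ = 1.069, v = 0.285. Fall = 0.181 × 1.069 × 5 = 0.97 points; SD of change 2.9; ratio 0.332; P = 0.421; both arms 0.177; therapy only 0.244.

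**Step 3. The same by simulation**, with scores rounded and held within the scale. The mean falls by 0.9 to 3.4 points, one arm is significant in about 41% to 99.5% of trials, and both arms in about 16% to 99%.

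**Step 4. Both scales together, with the entry rule varied.** Percentage of null trials in which both arms are significant, EPDS/GAD-7 (4000 trials per setting):

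| Entry rule | Means EPDS/GAD-7 | ρ = 0.5 | ρ = 0.7 | ρ = 0.819 |
|---|---|---|---|---|
| Either scale | 7/5 | 81/94 | 47/64 | 21/34 |
| Either scale | 10/8 | 28/47 | 11/20 | 5/9 |
| Both scales | 7/5 | 100/100 | 97/92 | 75/64 |
| Both scales | 10/8 | 96/89 | 70/54 | 36/26 |
| Either, MINI also selecting on the stable trait | 7/5 | 42/57 | 16/23 | 7/10 |
| Either, MINI also selecting on the stable trait | 10/8 | 3/4 | 1/1 | 0/0 |

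The last two rows model the MINI as requiring a stable component more than 1 SD above its mean.

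**Step 5. Shared improvement.** If both arms also improve by an assumed 0.3 SD, the closed form of Step 2 puts both arms significant in 99% or more of trials, for every cut-off from 0.4 to 1.4 SD above the mean and every ρ from 0.3 to 0.9.

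**Step 6. The discordant pattern.** P(1 − P) is largest at P = 0.5, where it is 0.25; that needs a fall of about 0.37 SDs of change. The simulations gave up to 26%. In the same null trials the between-arm test on change scores rejected in 4.4% to 5.5%, in either direction.

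**The case against.** The strongest reply is that the plan does not judge therapy by these tests. They stand beside the descriptive summaries, in permissive wording. Trial Design defines success against the control group, and Analytic Methods calls the between-arm difference in change the essential question. That stands. A reader might infer that the plan rests its efficacy claim on within-arm tests, or that regression to the mean biases the between-arm analyses. The documents support neither: randomisation makes the regression equal in expectation in both arms.

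A reader might also infer that both arms will probably be significant from selection alone. That too goes beyond the documents. They give no screened mean or SD, no 19-week correlation and no natural-course data, and they state the entry rule in two ways. Phase II goes only to mothers already positive at Phase I, which should raise the pool mean and reduce regression. The MINI diagnosis is a further filter, less tied to the single score. Under some of these settings both-arm significance is rare.

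R-DAS is not a qualifying scale, so the selection argument does not reach it. A within-arm test on R-DAS still cannot show an effect of therapy.

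What the reply does not remove is that p-values unable to answer the stated question are planned with no statement that they are not evidence, while the between-arm method is left unfixed. The discordant pattern also needs no large regression to the mean; it is most frequent when the fall is moderate.

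**Conclusion.** The point holds as one of interpretation, of moderate weight. Pre-post tests are planned in each arm, and none can show an effect of systemic therapy on any of the three scales. For EPDS and GAD-7 a fall is expected in both arms through selection on the apparent baseline and through care that both arms receive.

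The size depends on the assumptions. From selection alone, with entry on GAD-7 at 10 or more, both arms are significant in about 16% to 99% of trials. The figure is lower, down to a few per cent or less, if entry is on either scale, the pool is more severe and the MINI selects on stable severity. It is near certain only with an added, assumed shared improvement. Significance in the therapy arm alone can occur in up to about a quarter of null trials, against about 5% rejection for the between-arm test. The between-arm analyses remain valid.

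**What to change.** In Analytic Methods:

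1. Remove the paired t and Wilcoxon signed-ranks tests as inferential steps for EPDS, GAD-7 and R-DAS.
2. Report pre and post summaries, mean change with its confidence interval, and the planned boxplots by arm, as description only.
3. State that any claim for therapy rests solely on the between-arm difference from ANCOVA of the post score with baseline as covariate. This is already the third listed option. Fix it in advance in place of a later choice among three; the Protocol itself notes its gain in power.
4. Reword the condition that leads to the stepwise regression, which refers to significant improvement at post-testing, so that it does not lean on a within-arm p-value.

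Separately, reconcile the either-scale and both-scales entry rules, and say explicitly whether Phase II supplies the pre-scores.

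The cost is the loss of the within-arm p-values and of the freedom to choose the between-arm method later. No extra data are needed and there is no burden on the mothers.

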#### **Analytic Methods**

The analysis of the data will be conducted by the Statistical Package for the Social Sciences, IBM SPSS 28 and R Studio.

RCT 1 the antenatal period: Provide the evidence as to whether an intervention to support mothers who are suffering from anxiety or depression during the antenatal period will make a significant difference to these mothers viz a viz the parents in the control group

Baseline characteristics will be compared between the two groups (Intervention/Control) to observe whether the two groups showed any demographic differences. To assess baseline participant differences, binominal logistic regression will be used to test for demographic differences across the two study groups – the intervention group and the control group. Any baseline demographic factor that differed between the two groups at p < 0.10 will be included as a potentially confounding variable in follow-up models testing for the effect of the intervention. Effect sizes will be given in terms of odds ratios for analyses using binomial logistic regression, , with 1 meaning no difference, values under 1 meaning less likely, and values over 1 meaning more likely to occur in the intervention compared to control group. However, this approach will be feasible if there is enough detail to conduct such analysis for certain demographic variables. If such problem arises, alternatively, a Chi-Square test of association will be carried out by selected demographic variables to see whether the two groups showed any demographic differences. The null hypothesis specifies that there is no association between the two variables and will be accepted if the p-value exceeds the 0.05 level of significance. The effect size for the chi-square test was measured using Cramer's V.

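### The optional three-class change comparison uses an unordered chi-square for a directional question; an ordinal test on the same classes would answer it with more power (minor)

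*Protocol*

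**What the plan says.** Analytic Methods introduces the classes after the boxplots and the paired tests: "The change of the pre- and post-test scores can be categorized into three groups as no change, lower". A rise in the score is the third class. The plan for testing the two arms against each other is that these classes are "compared through the Chi-Square test between intervention and control to assess whether the increase or decrease in the post-test score is differing". For this comparison the protocol names no trend, ordinal or small-cell version of the test.

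The following paragraph turns to the treatment effect proper: "Next, to assess the effect of the study condition, there are three adequate ways to analyse a numerical outcome". It lists a t-test or Mann-Whitney test on change scores, a mixed-model ANOVA, and ANCOVA on the post-intervention score.

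The trial is small. The Trial Flow Chart states "60 mothers will be randomised", with "30 in intervention group" and as many in the control group. The significance rule is "Results will be determined to be statistically significant if p values were <0.05". Trial Design gives the expected direction: lower EPDS and GAD-7 scores and higher R-DAS scores in the intervention arm.

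**The concern.** Lower, no change and higher form an ordered scale, and the comparison is meant to show whether scores move up or down differently in the two arms. The Pearson chi-square asks only whether the two arms differ in any way across three labels. A difference confined to the middle class counts as much as a shift from worse to better. Two things follow: a significant result does not by itself say in which direction the arms differ, and a real shift towards improvement is detected less often than with a test that uses the order. In a trial of 60 mothers, a between-arm p-value of this kind could be reported beside the main analysis and appear to disagree with it.

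**Working it through.** **Inputs from the protocol.** Three classes, two arms, 30 mothers per arm, significance at 0.05. Degrees of freedom = (2 - 1) x (3 - 1) = 2. The protocol gives no SD of change, no class shares and no power figure, so there is nothing to reproduce, and every class share below is an assumption.

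**Step 1: the statistic ignores order (no assumption about shares needed).** Take two illustrative tables, with counts in the order lower / no change / higher:

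- Table A: intervention 27/2/1, control 20/3/7.
- Table B: intervention 27/1/2, control 20/7/3. This is table A with the last two classes exchanged.

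With equal arms, each class adds 2 x (observed - expected)^2 / expected. For table A the class totals are 47, 5 and 8, and the expected counts per arm are 23.5, 2.5 and 4:

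2 x 3.5^2/23.5 + 2 x 0.5^2/2.5 + 2 x 3^2/4 = 1.04 + 0.20 + 4.50 = 5.74, p = exp(-5.74/2) = 0.057.

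Table B has the same three terms in another order, so again 5.74 and p = 0.057.

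Now the tie-corrected Wilcoxon-Mann-Whitney test:

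- Variance in both tables = (30 x 30/12) x [61 - sum(t^3 - t)/(60 x 59)], with tie groups of 47, 5 and 8. This is 75 x (61 - 104,400/3,540) = 2,363, so the SD is 48.6. The expected rank sum is 30 x 61/2 = 915.
- Table A: midranks 24, 50 and 56.5. Rank sum = 27 x 24 + 2 x 50 + 56.5 = 804.5; z = -110.5/48.6 = -2.27; p = 0.023.
- Table B: midranks 24, 51.5 and 58. Rank sum = 27 x 24 + 51.5 + 2 x 58 = 815.5; z = -99.5/48.6 = -2.05; p = 0.041.

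The ordinal test separates the two tables; the chi-square cannot.

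**Step 2: level and power.** These were found by enumerating every pair of tables at 30 per arm and adding the probabilities of those with p < 0.05.

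| Assumed shares (lower/none/higher, %) | Chi-square | Tie-corrected Wilcoxon |
|---|---|---|
| Both arms 76/6/18 (level) | 3.8% | 5.0% |
| Both arms 85/5/10 (level) | 3.3% | 5.2% |
| Both arms 70/8/22 (level) | 4.3% | 5.0% |
| Both arms 90/4/6 (level) | 2.4% | 5.1% |
| Control 70/8/22, intervention 90/4/6 (power) | 40% | 52% |
| Control 60/10/30, intervention 85/5/10 (power) | 50% | 61% |

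**Step 3: a different set of assumptions.** Let change be a rounded normal variable with SD 3 to 7 and control mean 0, -1.5 or -3, and compare the chi-square with a linear trend test (scores -1, 0, 1).

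- Level: 3.8% to 4.9% for the chi-square; 5.0% to 5.2% for the trend test.
- Power at a standardised effect of 0.5: 14% to 28% against 22% to 37%, a gap of about 7 to 9 points.
- Power at 0.8: 28% to 61% against 42% to 71%, a gap of about 10 to 15 points.
- Power of a t-test on the numerical change score: 49% at 0.5 and 87% at 0.8.

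**Step 4: how thin is the middle class?** In the step 3 scenarios with no effect, its share is about 5% to 13%, or 30 x 0.052 = 1.6 to 30 x 0.132 = 4.0 mothers per arm. Both cells are below an expected count of 5. If one third of mothers had no change, the level of the chi-square would be 5.1%.

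**The case against.** The strongest reply is that little depends on this test. The protocol says only that change can be categorised, and the paragraph that follows assigns the treatment effect to the numerical scores. Those analyses use far more of the information: at SD 5, control mean -3 and effect 0.8, the power is 44% for the chi-square, 56% for the ordinal test on the classes and 87% for the numerical change. A Mann-Whitney test on the uncategorised change is already planned as the nonparametric option. This stands, and it limits the point to a minor one.

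Four stronger readings are tempting but not supported:

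- *The test is invalid because the middle class is nearly empty.* That rests on a distribution of change that the protocol does not give. The class is probably sparse, but the effect is mild conservatism with no inflation of false positives. The 2.4% figure needs 90% of mothers to improve in both arms.
- *An exact test is the remedy.* Under the four null cases in the table, the fully conditional exact Wilcoxon has a level of 1.4% to 4.0%, lower than the chi-square in each.
- *The baseline fallback repeats the error.* The protocol says "If such problem arises, alternatively, a Chi-Square test of association will be carried out by selected demographic variables". Those comparisons have no stated direction, no sparse table is shown, and a small-cell alternative is detail that a SAP commonly supplies.
- *The effect size for the change classes is also undirected.* "The effect size for the chi-square test was measured using Cramer's V" belongs to the baseline comparison. No effect size is prescribed for the change classes.

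**Conclusion.** The point holds as a minor one. The mismatch between an unordered test and a directional question follows from the protocol's wording and needs no assumption. The cost, roughly 7 to 15 points of power against an ordinal test on the same classes, does depend on assumed class shares at 30 per arm, although the ordinal test was ahead in every scenario tried. The level, about 2.4% to 4.9%, is secondary. A reader might infer that the trial's test of the treatment effect is weakened. The documents do not support that, because this comparison is optional and the effect is assessed on the numerical scores.

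**What to change.** In the Analytic Methods paragraph on change classes:

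1. Replace the chi-square by a Wilcoxon-Mann-Whitney test on the three ordered classes (tie-corrected or mid-p), or by a linear trend test. Name one in advance. The fully conditional exact form is not advised here, for the reason given above.
2. Report the between-arm difference in the proportion improved with a 95% CI. Improved means lower for EPDS and GAD-7 and higher for R-DAS, in line with Trial Design.
3. State that this comparison is supportive and that the treatment effect is judged on the numerical scores.

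The cost is a few words in one paragraph. No new data are needed, and the tests are standard in R, which the protocol already names. The baseline comparison needs no change on this account.

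### The protocol leaves the main between-group analysis open between change scores and ANCOVA, with no rule or time point for choosing, although it says itself that ANCOVA increases power

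*Protocol*

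**What the plan says.** The Analytic Methods section lists three ways of assessing the study condition on GAD-7, EPDS and R-DAS and introduces them with the remark that "the prescores must be considered (the best approach will be chosen accordingly"). They are:

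- Item 1: an independent-samples test on post-minus-pre change, with a non-parametric fallback: "If a nonparametric approach is chosen (assuming normality assumption is deviated), the Mann-Whitney test should be performed on change scores".
- Item 2: a two-way mixed ANOVA. The protocol notes that its interaction p-value equals that of the t-test in item 1.
- Item 3: ANCOVA of the post score on the baseline score, of which it says: "ANCOVA adjusts the pre-test scores, increasing the power to determine whether or not there has been a treatment effect".

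The section ends with a normality check covering everything before it: "The assumption of normality to perform all the above tests will be evaluated by the Shapiro-Francia test". The general threshold is "Results will be determined to be statistically significant if p values were <0.05", whereas item 1 asks only for this: "The overall test is statistically significant if it yields a sufficiently small p-value". The flow chart gives the size as "60 mothers will be randomised", 30 to each arm.

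**The concern.** Item 2 describes the comparison of change between arms as the study's essential question, yet the protocol does not determine how it will be tested. It addresses the choice of method and leaves it open, so this differs from a detail on which a protocol is silent. Two things are at stake.

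- **Error rate.** If the method may be picked among correlated tests after their results are known, the chance of a false positive exceeds the nominal 5%.
- **Precision.** Choosing change scores would give away information from a baseline measurement that every mother provides before randomisation. In a trial of 60 that loss can matter.

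The normality check adds a third uncertainty. It can move the report from a mean difference to a rank test on change scores, which gives no mean difference and has no regression adjustment for baseline.

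**Working it through.** **Inputs from the protocol.** 30 mothers per arm; three outcomes; threshold 0.05 (taken as two-sided, since sidedness is not stated). The protocol gives no effect size, SD, power or pre-post correlation, so there is no sample-size figure to reproduce. The correlation r is an assumption, shown over 0.3–0.7.

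**Step 1: how many distinct choices.** The protocol's statement that items 1 and 2 agree was checked on one simulated data set: t² = F = 0.1447, and p = 0.7050 from both. The open choice is therefore change score versus ANCOVA, plus Mann-Whitney if normality is rejected.

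**Step 2: false-positive rate per outcome.** Simulation under no effect, 30 per arm, 20,000 trials per setting (Monte Carlo standard error about 0.15 percentage points), with normal or skewed (exponential) post-score error:

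| Analysis | r = 0.3 (normal / skewed) | r = 0.5 | r = 0.7 |
|---|---|---|---|
| Change-score t alone | 4.9% / 4.5% | 4.9% / 5.1% | 5.1% / 4.9% |
| ANCOVA alone | 4.9% / 4.8% | 4.9% / 4.9% | 4.8% / 4.9% |
| t or Mann-Whitney by normality test | 5.1% / 4.8% | 5.0% / 5.2% | 5.3% / 5.1% |
| Smaller p of change-score t and ANCOVA | 7.7% / 7.5% | 7.1% / 7.3% | 6.7% / 6.8% |
| Smaller p of switched test and ANCOVA | 7.9% / 8.0% | 7.2% / 8.0% | 6.8% / 7.5% |

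Each test alone, and the normality switch alone, stays close to 5%. Taking the smaller p gives roughly 6.5–8%.

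**Step 3: precision on a scale not used for selection (R-DAS).** With equal pre and post variances set to 1, the variance is 2(1 − r) for change and 1 − r² for ANCOVA. The ratio is 2(1 − r)/(1 − r²) = 2/(1 + r):

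- r = 0.3: 2/1.3 = 1.54
- r = 0.5: 2/1.5 = 1.33
- r = 0.7: 2/1.7 = 1.18

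In terms of power, for an assumed effect of 0.6 SD the same simulation (normal errors) gives change score versus ANCOVA 0.49 v 0.66, 0.63 v 0.74 and 0.84 v 0.89 at these correlations.

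**Step 4: precision on a scale truncated by its own cut-off (EPDS, GAD-7).** If only high baselines enter, the baseline variance V falls and the ratio becomes [(1 − r²) + (1 − r)²V]/(1 − r²) = 1 + V(1 − r)/(1 + r). For a standard normal baseline, V is 0.195 if the top 15% enter and 0.265 if the top 30% enter (both fractions assumed):

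- r = 0.3: 1 + 0.538 × V = 1.10 to 1.14
- r = 0.5: 1 + 0.333 × V = 1.06 to 1.09
- r = 0.7: 1 + 0.176 × V = 1.03 to 1.05

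The excess is thus about 3–14%. The Inclusion Criteria admit a mother on either scale, so strict truncation on each scale separately is a simplification. A weaker restriction would leave a larger V, and so a larger excess.

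**The case against.** The strongest reply is that the protocol nowhere says the choice follows sight of the results. It gives no time point, and a separate analysis plan may name one method in advance. A choice made without knowledge of the p-values keeps about 5%. This stands: the inflation is a worst case that the wording permits, not a planned procedure. It does not remove the point, because the protocol takes up the choice of method and settles nothing.

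Several stronger readings are tempting, and the documents do not support them:

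- **That the normality pre-test costs the 5% level.** Step 2 shows 4.8–5.3% for the switch alone. What it leaves unfixed is the effect measure.
- **That Mann-Whitney is a third free pick.** Item 1 allows it only when normality fails.
- **That normality is rejected about as often as a coin toss.** High rejection rates need change scores that are themselves clearly skewed, and the protocol gives no distribution. Differencing can cancel much of the skew in the separate scores.
- **That the error rate reaches about 20%.** Over three outcomes, simulation gives 17–22% with method picking, but already 12–14% with ANCOVA fixed (assumed between-outcome correlation 0.3–0.6). Most of the excess over 5% is multiplicity, a separate issue.
- **That the Mann-Whitney effect size is wrong.** It is described as "dividing the standardised test statistic z and square root of the number of pairs n". A two-group rank test has no matched pairs, but each mother supplies one pre-post pair, so n can naturally mean all 60. The wording is unclear rather than shown to be in error.

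**Conclusion.** The concern holds in this form: the main between-group analysis is not determined, and the protocol does not commit to the method that it credits with more power.

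If the choice followed the results, the false-positive rate per outcome would be at worst about 6.5–8% instead of 5%. If it were made blind to them, about 5%. If change scores were chosen, the variance would be 18–54% higher than under ANCOVA for R-DAS, and about 3–14% higher for a scale truncated by its own cut-off.

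These sizes rest on assumed correlations of 0.3–0.7, equal pre and post variances and, for the truncated case, an assumed top 15% or 30% entering. A reader might infer that the 5% level is certainly lost. The text shows only that it is not protected.

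**What to change.** In Analytic Methods, replace the parenthesis about choosing the best approach with: *For EPDS, GAD-7 and R-DAS the between-group effect is estimated by ANCOVA of the post score on arm and the baseline score of the same scale, reported as adjusted mean difference with 95% CI.*

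Then:

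- State that the normality test does not switch this analysis. If residuals are non-normal, use a bootstrap interval for the ANCOVA effect. The 5000-replicate bootstrap is at present attached only to the stepwise regression on change scores, which runs only after a significant improvement, so it would have to be extended to ANCOVA.
- Label the change-score, Mann-Whitney, categorised-change chi-square and stepwise-regression results as sensitivity or secondary analyses, so that none can stand in for the main one.
- State that n in the Mann-Whitney effect size is the total number of mothers in both arms.

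The cost is wording only, with no new data, provided it is done before the outcomes are analysed. It does not deal with multiplicity over the three outcomes, which needs its own decision.
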